15.2.1. SECONDARY EFFICACY VARIABLES & DERIVATIONS

Change from baseline calculation will be done as defined in [Section 6.6](#).

15.2.1.1. HbA1c

The measurement will be performed by the central laboratory for efficacy and safety samples.

15.2.1.2. Fasting plasma glucose

The measurement of fasting plasma glucose will be performed by the central laboratory for efficacy and safety samples. 'Fasting' is defined as no intake of food or drink (except water) for at least 10 hours.

15.2.1.3. Change in 8-point SMBG profile from baseline

8-point SMBG profile measurements will be performed by the patient at home and recorded in the patient diary, A single 8-point SMBG profile set includes measurements of SMBG values on 3 days, performed in the week preceding the next visit (of the three days, 2 should be consecutive). The patient should document the 3 pre-visit measurements in the diary, and will be advised to similarly document any additional estimations.

Individual pre-meal, individual post-meal, individual 2-hour excursion after meal, bedtime, overall (average) pre-meal, overall post-meal, overall excursion, 4-point average (pre-meal + bedtime), and daily average at scheduled visits will be computed.

For overall mean of blood glucose (BG), values for the SMBG profiles will be averaged over the specific time points in a day. Then this averaged value per day will be averaged across three days. The missing values will not be imputed. The daily average SMBG will not be computed for a day if the SMBG measurement was missing for more than 3 time points on a particular day. The SMBG overall average will be kept missing if the daily average is missing for all three days. If SMBG average is missing for one or two days, the SMBG average of the remaining days will be considered for the computation.

The average SMBG value across the three days at a particular visit and time point will be considered for the SMBG values at specific time points. For individual pre-meal, the average of pre-breakfast, pre-lunch and pre-dinner measurements within a day will be considered. The individual pre-meal values will be averaged across three days for overall average of pre-meal values. The individual post meal and overall post meal values will be computed in the same manner.

SMBG individual excursion values will be obtained by subtracting post-meal values with pre-meal values, it will be

Document:	\\JEEDC-NAS01A\Biosdata\Mylan\INSULIN_GLARGINE\UXA25824\Biostatistics\Documentation\SAP		
Author:	[name] and [name]	Version Number:	Final V1.0
		Version Date:	[27JUL2016]

Template No: CS_TP_BS016 – Revision 3
Effective Date: 01May2012

Reference: CS_WI_BS005

Copyright © 2012 Quintiles Transnational Corp. All rights reserved.

The contents of this document are confidential and proprietary to Quintiles Transnational Corp. Unauthorized use, disclosure or reproduction is strictly prohibited.

applicable for morning excursion, noon excursion and evening excursion on the respective days. For overall excursion at morning, afternoon and evening, the individual excursion values obtained on each day will be averaged across three days.

For 4-point average, pre-meal and bedtime SMBG measurements will be averaged for a particular day and then this average value will be averaged across three days.

15.2.1.4. Daily insulin dose/unit body weight (daily prandial injectable, basal insulin and total) for days of 8-point profiles

Patients will be asked to document the dose of Mylan's insulin glargine/Lantus® and insulin lispro taken on the days when they perform 8-point SMBG profiles (from week 0 to week 36). Doses will be recorded in the patient diary. This data will be transcribed to the eCRF after the patient diary is collected, by the investigator or designee at scheduled visits. The patient should document the 3 pre-visit estimations in the diary; and will be advised to document any additional estimations.

There will be three dose variables – daily prandial insulin, basal insulin dose and total insulin dose.

Daily prandial insulin dose (meal time insulin dose) per day is the sum of all the daily prandial insulin dose for a day and then averages for number of days measured.

Basal insulin dose is the average of the insulin glargine or insulin Lantus dose over days measured. If the basal insulin dose is missing for a particular day of collection, total insulin dose will not be computed for that day. The total insulin dose will be computed for the remaining days were basal insulin dose is collected. The total insulin dose available at the remaining days will be used for the computation of average total insulin dose. For the computation of total daily prandial doses, the patients with at least three daily prandial doses at a particular day are considered. Total daily prandial dose will not be computed for a day if the daily prandial dose is recorded less than 3 times in a day and the total daily prandial dose computed at the remaining days will be used for the computation of average total daily prandial dose across the days.

Total insulin is the sum of daily prandial and basal insulin and then averaged for days measured. The missing insulin doses will not be considered for the average computation. All dose will be divided by total body weight (kg) to convert to daily insulin dose (U)/unit body weight (kg).

15.2.2. MISSING DATA METHODS FOR SECONDARY EFFICACY VARIABLES

Not applicable.

15.2.3. ANALYSIS OF SECONDARY EFFICACY VARIABLES

15.2.3.1. Analysis of change from baseline in HbA1c

Descriptive statistics for HbA1c will be presented by treatment sequence group for actual and change from baseline (week 52 result from MYL-GAI-3001) to scheduled visits.

Treatment sequence group comparison will be done using the MMRM model, including treatment sequence, visit, treatment sequence-by-visit interaction, region as fixed effects, and baseline values as covariates.

Document:	\\JEEDC-NAS01A\Biosdata\Mylan\INSULIN_GLARGINE\UXA25824\Biostatistics\Documentation\SAP	Version Number:	Final V1.0
Author:	[name] and [name]	Version Date:	[27JUL2016]

Template No: CS_TP_BS016 – Revision 3
Effective Date: 01May2012

Reference: CS_WI_BS005

Copyright © 2012 Quintiles Transnational Corp. All rights reserved.

The contents of this document are confidential and proprietary to Quintiles Transnational Corp. Unauthorized use, disclosure or reproduction is strictly prohibited.

LS means for each treatment sequence group and associated standard errors will be derived. Differences in LS means will be calculated and associated 2-sided 95% confidence intervals (p-value, as required) will be provided. These will be derived from the calculation of Type III sum-of-square and LS means from MMRM model.

For graphical display at each visit, LS means and 95% CI will be generated from the MMRM model including treatment sequence group, visit, treatment- sequence group by-visit interaction, region as fixed effects, and baseline values as covariates. In addition, mean (\pm SD) plot will be prepared for actual HbA1c measurements by visit.

15.2.3.2. Analysis of change from baseline in fasting plasma glucose

Descriptive statistics will be presented by treatment sequence group for actual and change from baseline (week 52 result from MYL-GAI-3001) to scheduled visits for fasting plasma glucose.

Treatment sequence group comparison will be done using the MMRM model, including treatment sequence group, visit, treatment sequence group-by-visit interaction, region, as fixed effects, and baseline values as covariates.

LS means for each treatment sequence group and associated standard errors will be derived. Differences in LS means will be calculated and associated 2-sided 95% confidence intervals (p-value, as required) will be provided. These will be derived from the calculation of Type III sum-of-square and LS means from MMRM model.

15.2.3.3. Analysis of Change in 8-point SMBG profile from baseline

8-point SMBG profile at a visit will be calculated using available pre-visit measurements in the diary (performed in the week preceding the visit), as defined in [Section 15.2.1.3](#).

Descriptive statistics will be presented by treatment sequence group for actual and change from baseline (week 52 result from MYL-GAI-3001) to scheduled visits for SMBG profile.

Treatment sequence group comparison will be done using the MMRM model, including treatment sequence group, visit, treatment sequence group-by-visit interaction, region, as fixed effects, and baseline values as covariates.

LS means for each treatment sequence group and associated standard errors will be derived. Differences in LS means will be calculated and associated 2-sided 95% confidence intervals (p-value, as required) will be provided. These will be derived from the calculation of Type III sum-of-square and LS means from MMRM model.

For graphical display at each period, LS means and 95% CI for daily mean of SMBG will be generated from the MMRM model including treatment sequence group, treatment sequence group -by-visit interaction, region, as fixed effects, and baseline values as covariates. In addition, mean (\pm SD) plot for daily mean of SMBG will be prepared for actual measurements by visit.

15.2.3.4. Analysis of Change in Daily insulin dose/unit body weight (daily prandial injectable and basal insulin) for days of 8-point profiles.

Descriptive statistics will be presented by treatment sequence group for actual and change from baseline (week 52 result from MYL-GAI-3001) to scheduled visits for insulin dose including basal insulin dose, daily prandial insulin dose, and total insulin dose.

Treatment sequence group comparison will be done using the MMRM model, including treatment sequence group, visit, treatment sequence group by-visit interaction, region, as fixed effects, and baseline values as covariates.

Document:	\\JEEDC-NAS01A\Biosdata\Mylan\INSULIN_GLARGINE\UXA25824\Biostatistics\Documentation\SAP		
Author:	[name] and [name]	Version Number:	Final V1.0
		Version Date:	[27JUL2016]

Template No: CS_TP_BS016 – Revision 3
Effective Date: 01May2012

Reference: CS_WI_BS005

LS means for each treatment sequence group and associated standard errors will be derived. Differences in LS means will be calculated and associated 2-sided 95% confidence intervals (p-value, as required) will be provided. These will be derived from the calculation of Type III sum-of-square and LS means from MMRM model.

For graphical display at scheduled visits, LS means and 95% CI for total daily insulin dose (meal time +basal) will be generated from the MMRM model including treatment sequence group, visit treatment sequence group-by-visit interaction, region, as fixed effects, and baseline values as covariates. In addition, mean (\pm SD) plot total daily insulin dose will be prepared for actual measurements by schedule visit.

15.2.4. SUBGROUP ANALYSIS

Not applicable.

16. QUALITY OF LIFE ANALYSIS

Not applicable.

17. SAFETY OUTCOMES

All outputs for safety outcomes will be based on the Safety Analysis Set. All safety output will be presented by treatment sequence group at each treatment period.

17.1. ADVERSE EVENTS

Adverse Events (AEs) will be coded using most updated MedDRA central coding dictionary, when it is available at time of analysis is conducted.

An AE is defined as any untoward medical occurrence in a patient or clinical investigation patient administered a pharmaceutical product that does not necessarily have a causal relationship with the product. An AE can therefore be any unfavorable and unintended sign (including a new, clinically important abnormal laboratory finding), symptom, or disease, temporally associated with drug administration, whether or not related to the product.

The above definition covers also cases of

- Exacerbation of pre-existing diseases or conditions.
 - Pre-existing diseases or conditions (reported at time of screening in medical history) will not be considered AEs unless there is an increase in the frequency or severity, or a change in the quality of the disease or condition.

An AE will be defined as treatment emergent (TEAE) if the first onset (or worsening in the case of pre-existing disease) is after the first administration of Mylan's insulin glargine sequence group or Lantus® sequence group (i.e. after the randomization) through 28 days after the last dose.

Document:	\\JEEDC-NAS01A\Biosdata\Mylan\INSULIN_GLARGINE\UXA25824\Biostatistics\Documentation\SAP		
Author:	[name] and [name]	Version Number:	Final V1.0
		Version Date:	[27JUL2016]

Template No: CS_TP_BS016 – Revision 3
Effective Date: 01May2012

Reference: CS_WI_BS005

See Appendix 1 for handling of partial dates for AEs. In the case where it is not possible to define an AE as treatment emergent or not, the AE will be classified by the worst case; i.e. treatment emergent.

An overall summary of number of patients for each treatment period within each of the categories described in the sub-section below, will be provided as specified in the templates.

Treatment sequence group comparison will be performed using Fisher's exact test for each treatment period. P-value for the corresponding two-sided test will be presented.

Listings will include TEAEs and Non-TEAEs.

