#### **Number of Patients:**

From approximately 70 selected sites, approximately 69 patients will be included in each arm, with a target of approximately 138 randomized patients in both arms together.

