## **9. DATA ANALYSIS/STATISTICAL METHODS**

### **9.1 Sample Size Determination**

Approximately 138 patients with type 1 diabetes will participate in this trial. Approximately 69 patients will be randomized to one of the two sequence groups (Mylan sequence group: Mylan's insulin glargine switch to Lantus® sequence group and switch back to Mylan's insulin glargine or Lantus Sequence Group: Lantus® to Lantus® to Lantus® sequence group) in a 1:1 ratio. No replacement of patient will be performed if patient discontinued prematurely from the study. For the modified intent-to-treat (mITT) population, power to demonstrate equivalence with  $\pm 0.4\%$  limits will be 90% with 10% patients who don't have at least one baseline and one last period HbA1c data. The power is calculated assuming no true mean group difference and a 0.61% standard deviation. This standard deviation is based on published results for clinical studies with Lantus® [12].

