2.2. SECONDARY OBJECTIVES

To compare treatment sequence group of Mylan's insulin glargine to Lantus®, at 36 weeks, when administered in combination with mealtime insulin lispro with respect to:

1. Change in basal insulin dose per unit body weight (U/Kg/day).
2. Immunogenicity: incidence and change from baseline in the relative levels of ADA, incidence and change from baseline in the relative levels of anti-HCP antibodies.
3. Rate of hypoglycemic events per 30 days; and occurrence of hypoglycemia
4. Occurrence of local reactions, systemic reactions and other adverse events.
5. Change in fasting plasma glucose from baseline.
6. Change in 8-point (self-monitored blood glucose) SMBG profile from baseline
7. Device related safety assessment.

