7.2. MULTICENTER STUDIES

This study will be conducted by multiple investigators at multiple centers globally. Randomization to treatment sequence arms is stratified by region.

Geographical region will be categorized as follows:

Geographic Region	Country
North America	United States of America, Canada

Document: \\IEEDC-NAS01A\Biosdata\Mylan\INSULIN_GLARGINE\UXA25824\Biostatistics\Documentation\SAP
Author: [name] and [name] Version Number: Final V1.0
Version Date: [27JUL2016]

Template No: CS_TP_BS016 – Revision 3
Effective Date: 01May2012

Reference: CS_WI_BS005

Copyright © 2012 Quintiles Transnational Corp. All rights reserved.

The contents of this document are confidential and proprietary to Quintiles Transnational Corp. Unauthorized use, disclosure or reproduction is strictly prohibited.

Europe	Latvia, Estonia, Slovakia, Czech Republic, Hungary, Germany
--------	---

A term for treatment by region interaction will not be included in the primary analysis model, however, a sensitivity analysis, based on the primary model but including a term for treatment sequence by region interaction, will be performed.

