15.1.3. PRIMARY ANALYSIS OF PRIMARY EFFICACY VARIABLE

The primary objective of this study is to test the equivalence of changes in HbA1C between two treatment sequence groups at week 36.

The primary efficacy analysis will be performed for the mITT population.

ANCOVA will be performed on the primary outcome variable and the model will include region and sequence group as fixed effect and baseline value (52 weeks in MYL-GAI-3001) as covariate using mITT population. A 95% confidence interval for the difference between two treatment sequence groups for mean change from baseline HbA1c at endpoint will be produced using the ANCOVA method. Equivalence of Mylan's insulin glargine sequence group to Lantus® sequence group will be established if the 95% confidence interval is within $\pm 0.4\%$ equivalence limits.

The Least Square (LS) means for each treatment sequence group and associated standard errors will be derived. Differences in LS means will be calculated and associated 2-sided 95% confidence intervals will be provided.

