17.6.2. IMMUNOGENICITY PROFILES ANALYSES

Following parameters will be summarized for immunogenicity.

- Total Insulin Antibodies
 - Percent Binding (%B/T, Continuous outcome)
 - Positive/Negative (Categorical outcome)
- Cross Reactive Insulin Antibodies
 - Percent Binding (%B/T, Continuous outcome)
 - Positive/Negative (Categorical outcome)

Document:	\\JEEDC-NAS01A\Biosdata\Mylan\INSULIN_GLARGINE\UXA25824\Biostatistics\Documentation\SAP	Version Number:	Final V1.0
Author:	[name] and [name]	Version Date:	[27JUL2016]

Template No: CS_TP_BS016 – Revision 3
 Effective Date: 01May2012

Reference: CS_WI_BS005

Copyright © 2012 Quintiles Transnational Corp. All rights reserved.

The contents of this document are confidential and proprietary to Quintiles Transnational Corp. Unauthorized use, disclosure or reproduction is strictly prohibited.

- Insulin(Drug) Specific Antibody
 - Percent Binding (%B/T, Continuous outcome)
- Anti-HCP
 - Positive/Negative (Categorical outcome)

Immunogenicity profiles with continuous variables (% binding) will be analyzed using the MMRM method for each assay, similar to change from baseline efficacy analyses. The model will include the terms region, treatment sequence group, visit, treatment sequence group-by-visit as fixed effects, and baseline value as covariate. The treatment sequence group difference and 95% confidence intervals will be constructed using the model at scheduled visits. In case the normal distribution assumption is severely violated, then non-parametric analysis will be performed using Wilcoxon rank-sum test for treatment sequence group comparison, Hodges Lehmann's estimator will be used to compute the median difference between the treatment sequence groups and the corresponding 95% confidence interval. Safety population will be used for ADA continuous variables. Immunogenicity profiles with dichotomous outcomes will be summarized with frequency and percentage at scheduled visits for each assay. Treatment sequence group comparison will be performed using Fisher's exact test. P-value for the two-sided test will be presented.

Correlation analyses of insulin cross-reactive antibodies with clinical factors such as HbA1c and insulin doses will be performed by treatment sequence group along with graphics to explore relationship of insulin antibodies with such factors for each assay method used. Additionally, mean (\pm SD) and median (IQR) for actual measurements by visit will also be presented.

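### Binary safety outcomes are compared by Fisher p-values with no between-group difference or confidence interval, so the plan does not show how large an excess on switching the data still allow

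*SAP*

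**What the plan says.** Protocol 1.1 sets the aim of showing equivalent efficacy and safety when one glargine product is substituted for the other. SAP 2.2 lists among the secondary objectives "Occurrence of local reactions, systemic reactions and other adverse events", along with antibody incidence, occurrence of hypoglycemia and device safety.

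For binary outcomes the planned comparison is as follows:

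- **Adverse events (SAP 17.1):** Fisher's "exact test for each treatment period. P-value for the corresponding two-sided test will be presented".
- **Antibody positivity (SAP 17.6.2):** Fisher's "exact test. P-value for the two-sided test will be presented", for each assay. Anti-HCP positivity also gets a Fisher p-value, by visit.
- **Abnormal laboratory, ECG and vital-sign categories (SAP 17.2, 17.3, 17.4):** a Fisher p-value.
- **Device events (SAP 17.6.1):** a Fisher p-value if there are enough events.
- **Hypoglycemia incidence:** Fisher by visit in Protocol 9.9.3. SAP 17.6.3 presents incidence without a difference or interval.

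Protocol 9.2.6 names only Fisher or chi-squared tests for categorical data. Frequencies and percentages by sequence are tabulated throughout.

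The main continuous safety variables are treated differently. Laboratory values, vital signs, antibody percent binding and hypoglycemia rate per 30 days get a between-sequence difference with a 95% CI. The primary endpoint is judged entirely from an interval: equivalence holds "if the 95% confidence interval is within $\pm 0.4\%$ equivalence limits".

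**The concern.** A two-sided Fisher test asks whether the data contradict equal incidence. The safety question here is the reverse: how much extra incidence could switching cause and still fit the data? A p-value does not answer that, and it is the only comparative statistic planned for these outcomes.

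The trial was sized for HbA1c, not for incidence. For uncommon events, a non-significant result is likely even when the true incidence in the switching group is two or three times that of the Lantus group. Protocol 1.1 and SAP 3 add weight, because both expect an effect of switching to show up as a discernible difference. That reasoning is only as good as the size of difference the analysis could discern, and for binary outcomes the plan never shows that size.

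**Working it through.** **Inputs.** Protocol 3.1 plans that "approximately 69 patients will be included in each arm, with a target of approximately 138 randomized patients in both arms together". For HbA1c, Protocol 9.1 gives the margin of ±0.4 and states "The power is calculated assuming no true mean group difference and a 0.61% standard deviation", with 90% power after a 10% non-evaluable share. Neither document gives an event rate for any safety outcome, so all incidences below are assumptions. They are modelled as one whole-study comparison at a full 69 per arm.

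**Step 1: the plan's own figure.** Evaluable patients: 69 × 0.9 ≈ 62 per arm. SE = 0.61 × √(2/62) = 0.1096, and 0.4/0.1096 = 3.65. Power for a 95% CI inside ±0.4 is 2Φ(3.65 − 1.96) − 1 = 90.9% (90.4% with the t distribution). The stated 90% reproduces. It covers HbA1c only.

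**Step 2: Fisher power for incidence.** Power = Σ Bin(a; 69, p_Mylan) × Bin(b; 69, p_Lantus), summed over all pairs (a, b) with two-sided Fisher p < 0.05.

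| Lantus sequence | Mylan sequence | Exact power |
|---|---|---|
| 3% | 9% | 18% |
| 5% | 10% | 11% |
| 5% | 15% | 40% |
| 10% | 20% | 30% |
| 10% | 30% | 81% |
| 20% | 40% | 68% |
| 25% | 50% | 82% |

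The low figures belong to uncommon events. A tripling from 10%, or a doubling from 25%, would usually be detected.

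**Step 3: what an interval adds.** Take 10/69 (14.49%) against 4/69 (5.80%). Fisher p = 0.157. The Wilson limits are 8.07% to 24.66% and 2.28% to 13.98%. Newcombe's interval for the difference of 8.70 points is:

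- Lower: 8.70 − √((14.49 − 8.07)² + (13.98 − 5.80)²) = 8.70 − 10.40 = −1.7
- Upper: 8.70 + √((24.66 − 14.49)² + (5.80 − 2.28)²) = 8.70 + 10.76 = +19.5

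The p-value says only that equality is not rejected. The interval says that an excess of 19 points is not excluded.

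**Step 4: range.** The largest excess that Fisher still leaves non-significant at 69 per arm, for some Lantus counts:

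| Mylan vs Lantus | Fisher p | Difference (points) | Newcombe 95% CI |
|---|---|---|---|
| 5 vs 0 | 0.058 | +7.2 | 0.6 to 15.9 |
| 10 vs 3 | 0.077 | +10.1 | 0.1 to 20.7 |
| 16 vs 7 | 0.066 | +13.0 | 0.5 to 25.4 |
| 25 vs 14 | 0.058 | +15.9 | 0.9 to 30.1 |
| 47 vs 35 | 0.056 | +17.4 | 1.0 to 32.5 |

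In these borderline rows the interval excludes zero while Fisher does not reject, because Fisher is conservative. An exact interval would be somewhat wider. With identical observed counts of 7 vs 7, the half-width is 10.7 points.

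**The case against.** The strongest reply is that nothing in either document says a non-significant Fisher test will be taken as similarity. The equivalence conclusion rests on the HbA1c interval. Safety incidence is secondary, has no margin and feeds no decision rule. This stands. A reader might infer from the equivalent-safety aim and the discernible-difference reasoning that p > 0.05 is meant to support interchangeability, but the documents state no such rule.

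Other points also stand in part:

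- **The report would not be empty.** Percentages by sequence are tabulated, so a crude difference can be worked out. What is missing is a prespecified estimate with its precision.
- **Intervals exist elsewhere.** Hypoglycemia rate and antibody percent binding, both close to the question of an insulin switch, already have differences with 95% CIs. It would be wrong to say that safety as a whole lacks them, or that every continuous outcome has a region-adjusted one: exposure gets a t-test, and the Wilcoxon/Hodges-Lehmann fallback has no region term.
- **The planned tests are by period or visit.** In period 2 both groups take Lantus (SAP 3), so the whole-study power figures do not describe each planned test.
- **Region is secondary.** "Randomization to treatment sequence arms is stratified by region" (SAP 7.2), and the Fisher tests ignore this. There are only two strata and no resulting bias has been shown.

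SAP 6.5 does not close the gap. It allows tests at 0.05 or 95% CIs as alternatives, without committing to an interval for any proportion.

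**Conclusion.** The concern holds for binary safety outcomes. The plan gives counts, percentages and a Fisher p-value, and nowhere a between-group difference with its interval. For assumed Lantus-sequence incidences of 3% to 10%, power to detect the doublings and triplings examined runs from 11% to 40%, except 81% for 10% vs 30%. Observed excesses of roughly 7 to 17 points, with upper limits of about 16 to 33 points, can still carry p > 0.05.

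These sizes rest on assumed event rates and on 69 patients per arm over the whole study. A reader might go further and infer that doubled or tripled incidence would generally be missed; the figures for commoner events contradict that. The HbA1c conclusion is unaffected. This is a weakness in how the safety comparison is reported, and it is cheap to correct.

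**What to change.** In SAP 17.1, 17.6.1, 17.6.2 and 17.6.3, name a short list of key incidence outcomes: any TEAE, any SAE, local and systemic allergic reactions, ADA positivity, anti-HCP positivity, any and severe hypoglycemia, and device-related events.

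For each, report the sequence risk difference (Mylan minus Lantus) with a two-sided 95% CI, both over the whole treatment period and by period. Use a score-type interval such as Miettinen-Nurminen, stratified by region where counts allow, and an exact interval when events are sparse. For the antibody outcomes, define what counts as positive over the whole period. Sparse SOC and preferred-term rows do not need intervals.

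Keep the Fisher p-values as descriptive. State that p > 0.05 is not evidence of similarity, and that interval and p-value may disagree near the boundary.

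The cost is SAP wording and one more column in a few tables, with no new data or patients. The downside is several intervals without multiplicity adjustment. They should be labelled descriptive, since no safety margin is set.
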